8. STATISTICAL METHODS

All data collected during this study will be presented in subject data listings. All statistical analyses will be performed using SAS® for Windows, version 9.4 or later.

8.1 Summarizing and Tabulating the Collected Data

All data collected will be summarized according to the variable type:

- Continuous data summaries will include:
 - O Descriptive statistics (n, mean, standard deviation, median, minimum and maximum) will be presented by treatment group
 - For inferential statistics, if the Normality assumption is met, t-test will be used and if the Normality assumption is not met, a non-parametric method will be used.
- Categorical data summaries
 - o Frequencies and percentages will be presented by treatment group.
 - o For inferential statistics Chi-square or fisher's exact test will be used.
- Time-dependent data: Kaplan Meier methods will be used to analyze time dependent data and to depict the time to event data.

8.1.1 Subject Disposition and Withdrawals

There will be a detailed accounting of all subjects that signed the informed consent to participate in this trial. The following will be summarized:

- The number of subjects who signed the informed consent
- The number of subjects who are screen failures
- The number of subjects who are treated
- The number of subjects who completed the study
- The number of subjects who discontinued

Reasons for discontinuation will also be summarized.

In addition, there will also be a listing of all discontinued subjects, which will provide the clinical trial center and the specific reason for discontinuation.

8.1.2 Protocol Deviations

The deviations occurring during the clinical trial will be summarized descriptively according to the following categories:

- Entrance criteria deviation
- Withdrawal criteria deviation
- Received wrong treatment or incorrect dose
- Received an excluded medication
- All other deviations

Additionally a by-subject listing of all deviations will also be prepared.

8.1.3 Demographics and Baseline Characteristics

Demographics and baseline characteristics (i.e., Age, Gender, etc.) will be summarized using appropriate descriptive statistics.

Medical history of the subjects will also be provided as a by-subject listing and included as a baseline characteristic.

8.1.4 Prior and Concomitant Medications

Prior and concomitant medications will be summarized for the Safety population. All prior and concomitant medications recorded in the CRFs will be coded to match Anatomic Therapeutic Classification (ATC) codes using the most recent version of World health Organization (WHO) drug dictionary.

Summaries will be prepared using the coded terms. All prior and concomitant medications recorded in the eCRFs will also be listed.

8.1.5 Treatment Administration

All the data from administration of study drug will be summarized and/or listed appropriately.

8.2 Analysis of Efficacy Data

The primary analysis will be conducted on the ITT population. The Per Protocol (PP) population will be used as a supportive analysis.

8.2.1 Primary Endpoint

The primary efficacy endpoint for this study is the incidence of \geq Grade II acute GVHD by Day - 100.

Chi-square/ Fisher's exact test will be used to compare the primary endpoint between the treatment groups.

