# 1.4.3.7 PRO 140-CD01 Study

PRO 140\_CD01 study (open-label, 40 subjects, multi-center) evaluated the efficacy, safety, and tolerability of PRO 140 monotherapy (350 mg subcutaneous injection weekly for up to 12 weeks) for the maintenance of viral suppression following substitution of antiretroviral therapy in HIV-1 infected patients (with exclusive CCR5-tropic virus). Participants in this study were experienced HIV-infected individuals who were virologically suppressed on combination antiretroviral therapy. Consenting patients were shifted from combination antiretroviral regimen to PRO 140 monotherapy for 12 weeks.

Forty (40) subjects (M/F: 37/3) with median age of 54.5 years (26-72) and median CD4 T-cell count of 604.5 cells/mm3 (365-1240) were enrolled in the CD01 study. Overall, twenty-two out of 40 (55%) enrolled subjects completed 12 weeks of PRO140 monotherapy without experiencing virologic failure. Virologic failure was defined as two consecutive HIV-1 RNA levels of ≥ 400 copies/mL separated by at least 3 days. Of the 40 enrolled subjects, 3 subjects were found to have Dual/Mixed (D/M) tropism [1 at baseline and 2 at the time of virologic failure] and 37 subjects were found to have exclusive CCR5-tropic virus. Fifty-nine percent (59%) of R5-exclusive subjects compared to zero percent (0%) of D/M subjects experienced virologic success within 12 weeks of PRO140 monotherapy (p=0.0465). All virologic failure subjects who had available lab data in both studies achieved viral suppression to < 400 HIV-1 RNA copies/mL, as well as viral suppression to 'Non Detectable' or < 50 HIV-1 RNA copies/mL after re-initiation of ART.

The by-subject analysis of PhenoSense® Entry Assay data for PRO140, maraviroc, and AMD3100 shows no significant changes in the post-treatment IC50 and IC90 values were noted when compared with baseline values in virologic failure and non-virologic failure groups of subjects. As the aggregate analysis shows, the subjects who experienced virologic failure had higher IC90 value for PR0140 at baseline compared to subjects without virologic failure. The mean IC90 for subjects who experienced virologic failure was higher (10.84 μg/mL) than the IC90 for subjects without virologic failure (6.70 μg/mL) in the CD01 study (p=0.0115).

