## 8.7.5 Efficacy Analysis

# 8.7.5.1 Primary Analysis

The primary analysis will be conducted on the ITT population.

The primary efficacy endpoint for this study is the incidence of  $\geq$  Grade II acute GVHD by Day - 100.

Chi-square/ Fisher's exact test will be used to compare the primary endpoint between the treatment groups.

All data from the secondary endpoints will be summarized and tabulated according to the variable type:

- Continuous data summaries will include:
  - O Descriptive statistics (n, mean, standard deviation, median, minimum and maximum) will be presented by treatment group
  - o For inferential statistics, if the Normality assumption is met, t-test will be used and if the Normality assumption is not met, a non-parametric method will be used.
- Categorical data summaries
  - o Frequencies and percentages will be presented by treatment group.
  - o For inferential statistics Chi-square or fisher's exact test will be used.

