4. SAMPLE SIZE DETERMINATION AND RATIONALE, STATISTICAL POWER, AND SIGNIFICANCE LEVEL

For this two arm clinical trial, it is planned to have a total of 60 subjects (30 per treatment group). This is a proof of concept study, and sample size is on the basis of clinical judgment and not based on statistical power calculation. The number of subjects was deemed adequate to provide clinically meaningful descriptive results consistent with study objectives. Based on literature review, the incidence of GVHD in ablative transplant population range from 40-60%. Assuming that the control incidence of GVHD is 50% and that of the Active group is 15%, a sample size of 30 subjects per group produces a two-sided 95% CI for the difference in proportions with a width of 0.44 (i.e.,95% CI of 0.13 – 0.57).

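### No confidence interval is planned for the primary treatment difference, although one is the only quantitative support for 30 per arm, and the primary test is left open between two that can split at that size

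*SAP*

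**What the plan says.** - **Sample size.** SAP section 4 states that "sample size is on the basis of clinical judgment and not based on statistical power calculation" and that the number is adequate for descriptive results. It then assumes 50% incidence on control and 15% on active and reports that "a sample size of 30 subjects per group produces a two-sided 95% CI for the difference in proportions with a width of 0.44", with limits 0.13 and 0.57. Protocol 8.3 gives the clinical-judgment statement alone, with no rates and no interval.
- **Primary analysis.** SAP 8.2.1: "Chi-square/ Fisher's exact test will be used to compare the primary endpoint between the treatment groups". Protocol 8.7.5.1 has the same sentence. Neither says which test applies when, or whether the chi-square carries a continuity correction.
- **Other planned output.** SAP 8.1 gives counts and percentages by arm for categorical data. SAP 8.3 repeats the primary method on the per-protocol set. SAP 7.4 plans a tipping-point analysis of the primary endpoint. None of these sections produces a CI for the difference.
- **Level.** Protocol 8.7 sets two-sided tests at a level printed as 0.05%. The SAP states no test level; its only interval is a 95% one.

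**The concern.** The primary objective is to assess efficacy against placebo, in a trial that disclaims a power calculation and describes its aim as descriptive. The most informative result for that aim is the size of the difference and its uncertainty. SAP section 4 recognises this by quoting an expected interval, but the analysis sections do not carry it through. The reader of the report would get two percentages and a p-value, and would have to work out the uncertainty alone.

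The p-value is also not fully specified. If the two candidate tests gave the same answer at this size, the slash would not matter. They do not always do so, and the tipping-point analysis cannot locate a tipping point until the test is fixed.

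**Working it through.** **Inputs.** n = 30 per arm; control 50%, active 15%; 95% two-sided interval; background incidence range 40 to 60% (all SAP section 4). Assumed: 5% two-sided test level, complete Day-100 outcomes, independent binomial counts, no use of the stratification factor.

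**1. The SAP's own figure.** Unpooled Wald, control minus active:
0.35 ± 1.96 × √(0.50×0.50/30 + 0.15×0.85/30) = 0.35 ± 1.96 × √(0.00833 + 0.00425) = 0.35 ± 0.220, that is 0.13 to 0.57, width 0.44. It reproduces.

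**2. The same interval by Newcombe.** Wilson limits (l, u) are 0.332 to 0.668 at 50% and 0.063 to 0.316 at 15%. With subscript 1 for control and 2 for active:
- lower = 0.35 − √((p₁−l₁)² + (u₂−p₂)²) = 0.35 − √(0.168² + 0.166²) = 0.113
- upper = 0.35 + √((u₁−p₁)² + (p₂−l₂)²) = 0.35 + √(0.168² + 0.087²) = 0.540

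The width is 0.43. For smaller effects the interval widens:

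| Control vs active | Wald width | Newcombe width |
|---|---|---|
| 50% vs 15% | 0.44 | 0.43 |
| 50% vs 25% | 0.47 | 0.45 |
| 50% vs 50% | 0.51 | 0.48 |

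**3. One table, three p-values.** Placebo 15/30, PRO 140 7/30: 22 events, so 11 expected per arm, and 19 expected non-events.
- Pearson, uncorrected: 2×4²/11 + 2×4²/19 = 4.59, p = 0.032
- Yates: 2×3.5²/11 + 2×3.5²/19 = 3.52, p = 0.061
- Fisher: p = 0.060
- Newcombe 95% CI, PRO 140 minus placebo: −0.47 to −0.02

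**4. What an interval adds.** Placebo 15/30, PRO 140 9/30: uncorrected chi-square 2×3²/12 + 2×3²/18 = 2.5, p = 0.11; Fisher p = 0.19. The Newcombe interval is −0.41 to 0.05. No effect and a large benefit are both compatible with these data, which 50%, 30% and a p-value do not show directly.

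**5. All tables.** Each of the 31 × 31 = 961 possible tables was tested at 5%, and probabilities were summed from the exact binomials.
- Uncorrected chi-square and Fisher split in 54 tables. In all 54, chi-square is significant and Fisher is not.
- In 38 of the 54, every expected count is 5 or more.
- Yates and Fisher split in none.

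| True rates (control, active) | Chi-square rejects | Fisher rejects | Split |
|---|---|---|---|
| 50%, 15% | 0.847 | 0.777 | 7.0% |
| 50%, 20% | 0.692 | 0.596 | 9.6% |
| 50%, 25% | 0.516 | 0.413 | 10.3% |
| 50%, 30% | 0.351 | 0.259 | 9.2% |
| 50%, 50% | 0.052 | 0.027 | 2.5% |

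At the ends of the SAP's background range with 15% on active, the split probability is 10.6% (control 40%) and 2.5% (control 60%).

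**6. The printed level.** Taken literally, 0.05% is 0.0005. Exact power at 50% versus 15% would then be 27.3% with uncorrected chi-square and 20.8% with Fisher.

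**The case against.** The other side has a good deal right.

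- **A reader might infer that the trial was sized on the interval.** The SAP does not say so. Clinical judgment set the number; the 0.44 describes precision at that number.
- **A reader might infer that the analysis yields only a p-value.** It does not. SAP 8.1 gives percentages by arm, so the point difference can be read off. What is missing is its interval.
- **A reader might infer that the open choice inflates the false-positive rate.** It barely can. Fisher never rejects where uncorrected chi-square does not, so even picking the test after seeing the data cannot exceed the chi-square's own error: 5.2% at a common rate of 50% and 4.9% at 40% or 60%. Nor do the documents say the choice will be made after unblinding; they do not say when it will be made.
- **The slash may mean the usual rule**, chi-square unless an expected count is below 5. If written down, that rule would settle the choice: at 50% versus 15% it calls for Fisher with probability only 0.09%. But it is not written, and it would still leave the continuity correction unstated.
- **A reader might cite the p-value for the earlier HIV study in Protocol 1.4.3.7.** That section names no test, and the comparison has three subjects in one group. It tells us nothing about a randomised 30 versus 30 comparison.

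What stands is the missing interval and the unspecified test, with a split that arises only if the chi-square is uncorrected.

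**Conclusion.** The point holds in a limited form. The one quantitative argument for 30 per arm is an interval that the planned analysis never reports, and the primary test is not determined by the text. The missing interval is the more important part. The open test alone would be close to missing detail: it changes the 5% verdict in about 7% of trials at the design rates and 9 to 10% at 50% versus 20 to 30%, and shifts power at the design rates from 0.85 to 0.78. These figures rest on a 5% level, which fits the SAP's 95% interval but not the 0.05% printed in Protocol 8.7, and on complete data in 30 subjects per arm. They do not mean that the trial is invalid or that its sample size is wrong.

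**What to change.** 1. **SAP 8.2.1.** Make the primary result the difference in Day-100 Grade II-IV incidence, PRO 140 minus placebo, with a two-sided 95% CI by one named method, for example Newcombe.
2. **Same section.** Name one test and state its continuity correction before unblinding, and use that test in the SAP 7.4 tipping-point analysis. Either candidate can be defended. Uncorrected Pearson chi-square has the higher power and agrees with the Newcombe interval in the 15/30 versus 7/30 example. With Fisher, that table gives an interval excluding zero beside a p-value above 0.05, which the SAP should anticipate.
3. **SAP section 4.** Describe the interval as expected precision at a number chosen by clinical judgment. Give widths by the method used in the analysis, including smaller effects: Newcombe 0.43 at 50% versus 15% and 0.45 to 0.48 at 50% versus 25 to 50%; if Wald is kept, 0.44 and 0.47 to 0.51.
4. **Protocol 8.7 and the SAP.** Reconcile the printed 0.05% level with the 95% interval, and state the level in the SAP.

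The cost is SAP wording, a correction or clarification of the protocol's level, and one more column in the efficacy table. Design, conduct and data collection do not change.

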8.2.2 Secondary Endpoints

All data from the secondary endpoints will be summarized as follows:

8.2.2.1 Incidence of severe and life-threatening (Grade III and Grade IV) acute GVHD by Day-100

The number and percentages of subjects with severe and life-threatening (Grade III and Grade IV) acute GVHD by Day-100 will be presented. Chi-square/Fisher's exact test will be used to compare the incidence between the treatment groups.

8.2.2.2 Incidence of organ-specific acute GVHD by Day-100

The number and percentages of subjects with organ-specific acute GVHD by Day-100 will be presented by organ category. Chi-square/ Fisher's exact test will be used to compare the incidence between the treatment groups.

8.2.2.3 Donor engraftment evaluated by T-cell and myeloid chimerism in peripheral blood

The number and percentages of subjects with donor engraftment failure evaluated by T-cell and myeloid chimerism in peripheral blood will be presented by different treatment groups. The definition of donor engraftment failure is presented in Section 7.9.8. Chi-square/ Fisher's exact test will be used to compare the incidence of donor engraftment failure.

8.2.2.4 Neutrophil and platelet count recovery

The number and percentages of subjects with neutrophil and platelet count recovery will be presented. The definition of neutophil and platelet count recovery is presented in Sections 7.9.5 and 7.9.6, respectively. Chi-square/ Fisher's exact test will be used to compare the incidence of neutrophil recovery and of platelet recovery between treatment groups.

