7.9.5 Definition and Duration of Platelet Recovery

Platelet recovery will be defined as post-transplant increase in platelet levels to greater than $20,000/\mu$ L on two consecutive counts at least 2 days apart. If no platelet transfusion is given on or between the days of the two counts, the second platelet count should be at least as high as the first.

Duration of platelet recovery will be defined as the difference between the date of transplant and the date of the first eligible count of the two consecutive counts.

Duration of Platelet Recovery = (Date of first eligible count – Date of transplant) +1

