7.9.6 Definition and Duration of Neutrophil Recovery

Neutrophil recovery will be defined as an increase in absolute neutrophil count (ANC) to greater than $500/\mu L$ on two consecutive days.

Duration of neutrophil recovery will be defined as the difference between the date of transplant and the date of the first count above the threshold (i.e., $500/\mu$ L) of the two consecutive days.

Duration of Neutrophil Recovery =

(Date of first count above the threshold – Date of transplant) +1

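### SAP 8.2.2.4 specifies only a test of the proportion with neutrophil and platelet recovery, with no time horizon, and leaves open whether and how the derived recovery times are compared

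*SAP*

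**What the plan says.** SAP 8.2.2.4 presents one result for this endpoint, "The number and percentages of subjects with neutrophil and platelet count recovery will be presented", and one comparison, "Chi-square/ Fisher's exact test will be used to compare the incidence of neutrophil recovery and of platelet recovery between treatment groups". It gives no time limit, whereas 8.2.2.1 and 8.2.2.2 both count events by Day 100.

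SAP 7.9.5 and 7.9.6 go further and derive a time for each cell line. For platelets, "Duration of platelet recovery will be defined as the difference between the date of transplant and the date of the first eligible count"; for neutrophils, "Duration of neutrophil recovery will be defined as the difference between the date of transplant" and the first count above the threshold. Section 8.2.2.4 refers to these sections only for the definition of recovery. (It also cites them in reverse order: 7.9.5 is platelets and 7.9.6 is neutrophils.)

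Two general rules could reach the durations. SAP 8.1 opens with "All data collected will be summarized according to the variable type". It then offers a t-test or non-parametric method for continuous data and states that "Kaplan Meier methods will be used to analyze time dependent data". Protocol 8.7.5.1 applies the continuous-data rule to all secondary endpoints. Within SAP 8.2.2, a between-arm time-to-event test is named only for GVHD-free survival (log-rank, 8.2.2.6), with censoring rules in 7.9.7.

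**The concern.** Protocol 8.2.2 lists the effect of study treatment on neutrophil and platelet recovery as a secondary efficacy endpoint, and Protocol 7.11.1 defines a date of recovery for each. Protocol 1.4.2 argues that CCR5 binding should not interfere with stem-cell homing, and time to recovery is evidence on that argument.

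A yes/no comparison with no horizon does not use the dates. If most subjects in both arms eventually recover, the two proportions will be close even if one arm recovers later. The plan would then report no difference from its one named test, and the analyst would have to decide after the fact whether to test the durations and how. The candidate methods treat non-recoverers and early deaths differently, so the choice can affect the answer.

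**Working it through.** **Plan's own figure.** The documents give no power or precision figure for recovery. The only one, in SAP section 4, concerns the primary endpoint. It reproduces as a Wald interval: 0.35 ± 1.96·√(0.50·0.50/30 + 0.15·0.85/30) = 0.35 ± 0.220, or 0.13 to 0.57, width 0.44. It has no bearing on this point.

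**Inputs.** From the documents: 30 per arm, two-sided tests. Assumed: alpha 0.05 (Protocol 8.7 prints 0.05%, but SAP section 4 uses a 95% interval); the same final recovery proportion in both arms, 90% to 97%; mean time to recovery 16 days, SD 4 to 6 days.

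**Step 1: how coarse the named test is.** If all 30 subjects recover in one arm and 25 of 30 in the other, the two-sided Fisher p-value is 2·C(30,5)/C(60,5) = 2·142,506/5,461,512 = 0.052. With 24 of 30 it is 2·C(30,6)/C(60,6) = 2·593,775/50,063,860 = 0.024. Six more failures are needed even against a perfect arm.

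**Step 2: the named test under a pure delay.** With equal final recovery the length of the delay does not enter the test. Summing the two binomial distributions over all tables with p ≤ 0.05 gives the chance of rejection:

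| Final recovery, both arms | Fisher rejects |
|---|---|
| 90% | 0.009 |
| 95% | 0.0015 |
| 97% | 0.0002 |

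**Step 3: a test on the times.** Simulation at 95% recovery, mean 16 days, 30 per arm, using a log-rank test that keeps non-recoverers at risk to the end. This approximates Gray's test, in which subjects with the competing event also stay in the risk set.

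| Delay | SD 6 | SD 4 | Fisher |
|---|---|---|---|
| 3 days | about 28% | about 49% | under 1% |
| 5 days | about 57% | about 85% | under 1% |

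A skewed distribution (median 16 days, log-SD 0.30, 95% recover) gives log-rank power of about 34%, 63% and 82% for delays of 3, 5 and 7 days, against about 0.2% for Fisher. Rounding each recovery up to the next scheduled visit changes these little (32%, 62%, 84%).

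**Step 4: cross-check by formula.** Schoenfeld: power = Φ(½·√D·|ln HR| − 1.96). With D = 0.95·60 = 57 recoveries and HR 0.5, ½·7.55·0.693 − 1.96 = 0.66, so power is 0.74. Over 54 to 60 recoveries the ranges are 0.92-0.94 (HR 0.4), 0.72-0.77 (HR 0.5), 0.47-0.51 (HR 0.6) and 0.26-0.28 (HR 0.7).

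**Step 5: what SAP 8.1 would do if applied.** A t-test or non-parametric test needs a duration for each subject. A non-recoverer has none, and SAP 7.3 rules out imputation, so the comparison would be among recoverers only. Kaplan-Meier could include everyone, but 8.1 names no variable and no between-arm test, and no section gives a rule for death before recovery. If such deaths were censored, the recovery curve would be overstated. Protocol 1.2 puts transplant-related mortality as high as 20-30% but does not say how much of it precedes recovery.

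**The case against.** The strongest reply is that the plan may already compare the times. SAP 8.1 covers all collected data, a duration in days is continuous, and Protocol 8.7.5.1 attaches a test to continuous secondary data. So a reader might infer that the recovery times are never compared, and the documents do not support that. What stands is that they leave the matter open: SAP 8.2.2 introduces its own endpoint-by-endpoint methods, and the one for recovery does not mention the durations.

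A reader might also infer that a delay could not be seen at all. That is too strong. SAP 8.4.3 summarizes blood count changes at each visit, with counts scheduled at Days 7, 14, 21 and 28 and then every two weeks to Day 112. A one-week delay would show there. These tables carry no test and do not apply the recovery definitions, so they soften the point without removing it.

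Nor do the endpoint lists speak of speed or time to recovery; they name count recovery. The case for analysing time rests on the dates and durations that the documents define. It is also fair that this is a proof-of-concept study sized for descriptive results, and that neutrophil recovery on two consecutive days needs counts beyond the scheduled ones. The existing definition already requires those.

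Finally, the formulas add one day, as in "Duration of Platelet Recovery = (Date of first eligible count – Date of transplant) +1", although the text calls the quantity a difference and transplant is Day 0. This is not a reason for concern here: it shifts both arms equally, matches the convention for GVHD-free survival in SAP 7.9.7, and changes no comparison.

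**Conclusion.** The point holds as a gap in the endpoint section. SAP 8.2.2.4 specifies one comparison, of a proportion with no horizon, and does not say whether or how the recovery times are compared. Under equal final recovery of 90% to 97%, that comparison has under a 1% chance of flagging a delay of any length. A log-rank or Gray-type test would have about 57-85% power for a 5-day delay and 28-49% for a 3-day delay at 95% recovery.

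The recovery rate, mean, SD and alpha behind these figures are assumptions. The size of the gain moves with them; the insensitivity of the named test follows from equal final recovery alone. A rank test that places non-recoverers last would give higher power under the same assumptions (79-98% for 5 days, 39-72% for 3 days), but those figures should not be credited to the Gray-type analysis proposed here. Even that analysis would often miss a 3-day delay.

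The change is worth making before database lock. It does not affect the primary endpoint.

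**What to change.** In SAP 8.2.2.4:

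- Name time from transplant to neutrophil recovery and time from transplant to platelet recovery as the compared variables.
- Analyse each by cumulative incidence, with death before recovery as a competing event and Gray's test between arms. Censor subjects who are alive and not recovered at their last assessment.
- Add the proportion recovered by a prespecified day for each cell line, with a 95% confidence interval for the difference between arms.
- Keep the ever-recovered table as description.
- Correct the order of the references to 7.9.5 and 7.9.6, and state that this section takes precedence over the general rules in 8.1 for these variables.

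If the day count is changed, change it everywhere, including GVHD-free survival in 7.9.7.

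The cost is SAP wording and one more secondary analysis of variables already derived. It adds tests to a plan with no multiplicity adjustment (SAP 7.6), so the result should be reported as supportive.
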